**Primary Outcome 2: The change in documented nadir hemoglobin not followed with an intraoperative transfusion.**

The hemoglobin of interest for this outcome is the lowest documented intraoperative hemoglobin for the case, for those who did not receive an intraoperative transfusion.

The analysis for this outcome will be conducted identical to that for Primary Outcome 1.

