We hypothesized that: 1) We would observe a reduction in pre-transfusion intraoperative hemoglobin, as a proxy for transfusion trigger, and reduction in nadir hemoglobin in cases where intraoperative transfusion was not performed. 2) A diminishing number of intraoperative transfusions would be observed, overall and at each hemoglobin value. 3) There would be a reduction in the nadir postoperative hemoglobin. 4) That any observed trends would be modulated by year, surgery type, institution and the presence of coronary artery disease. 5) That in the presence of a change in transfusion practice, we would not observe a change in mortality, post-operative myocardial injury or acute kidney injury.

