For those transfused, the hemoglobin analyzed will be the value immediately prior to the transfusion of the case. In the cases with multiple transfusions, it will be the highest of the identified pre-transfusion hemoglobin measures across each of the transfusions. We will define immediately prior to transfusion as the lab value drawn closest to transfusion within a 30-minute pre-transfusion window. If this proves too restrictive and more than 30% of pre-transfusion lab values will be excluded, the window will be liberalized to 45 minutes. The hemoglobin measurement identified is referred to as the “pre-transfusion hemoglobin” throughout this document. For those who were not transfused, the nadir hemoglobin will be the lowest value of the case.

The covariates to be included in all models (discussed below) are surgical specialty (defined based on anesthesia CPT Code assigned to the case), age, BMI, sex, presence of coronary artery disease (defined by ICD 9/10 codes), Elixhauser comorbidities, quarter of the study period, and nadir hemoglobin. The unit of measure for time used in trend analysis will be by quarter. The use of autologous blood will not be considered in this analysis. Patients who receive exclusively cell saver blood (and no PRBCs) will be considered not to be transfused for the purposes of the analysis.

We will describe the proportion of cases with a non-red blood cell blood product administered and the frequency of use of measures of coagulation (PT/INR, PTT, PLTs etc) as documented in the anesthesia record and the use of “cell saver” blood. Additionally, we will perform a survey of participating institutions to determine if formal blood transfusion protocols or blood transfusion management efforts, pre-operative preparation strategies were routinely used and which point of care coagulation tests were in place at the time the studied cases occurred.

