### **Primary Outcome 1: The change in documented hemoglobin prior to an intraoperative transfusion.**

The hemoglobin of interest for this outcome is the pre-transfusion hemoglobin. See additional definitions above. Additionally, for this primary outcome we will perform a sensitivity analysis, following the same statistical methodology, to compare the effect of including only the first transfusion of the case in those cases with multiple transfusion with our definition.

First, the trend of median pre-transfusion hemoglobin measurement by quarter will be assessed for any change over time by testing whether the slope is significantly different from 0 using a bivariate linear regression model with the dependent variable of median pre-transfusion hemoglobin measurement. If the slope is not significantly different from 0, then the analyses for this aim will conclude. Otherwise, a Joinpoint analysis will be conducted to determine if there are any inflection points in the trend. If no inflection points are found and the slope is negative and significantly different from 0, then Hypothesis 1 will be assumed true. If the Joinpoint analysis finds one or more inflection points in the data, then a Student's t test or Mann-Whitney U test will be used to compare the values between consecutive quarters to analyze the significance of the change. A similar analysis will be conducted at the institution level.

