## Sample Size:

Based on a rough approximation of the inclusion criteria using DataDirect, we found around 113,000 cases with intraoperative Hemoglobin/Hematocrit values, which should provide sufficient power for all planned analyses.

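### Primary Outcome 2 rests on non-transfused cases that had an intraoperative hemoglobin, so a change in who is tested can create or hide the hypothesised fall, and the primary decision rule does not allow for this

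*Protocol*

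**What the plan says.** Methods sets eligibility by age, surgical specialty and inpatient stay, with listed exclusions. Having an intraoperative hemoglobin is not among the criteria. For the nadir it says "For those who were not transfused, the nadir hemoglobin will be the lowest value of the case", and the Primary Outcome 2 section repeats this: "The hemoglobin of interest for this outcome is the lowest documented intraoperative hemoglobin for the case, for those who did not receive an intraoperative transfusion". A case with no sample has no value. The Sample Size section counts only cases that do have one: "around 113,000 cases with intraoperative Hemoglobin/Hematocrit values".

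The analysis is borrowed whole: "The analysis for this outcome will be conducted identical to that for Primary Outcome 1". Under Primary Outcome 1 this means "testing whether the slope is significantly different from 0 using a bivariate linear regression model with the dependent variable of median pre-transfusion hemoglobin measurement", that is, quarterly medians on time with no covariates. Two rules follow. One closes the aim on a null result: "If the slope is not significantly different from 0, then the analyses for this aim will conclude". The other confirms the hypothesis: "If no inflection points are found and the slope is negative and significantly different from 0, then Hypothesis 1 will be assumed true". Hypothesis 1 in the Introduction explicitly covers this outcome, since it predicts a "reduction in nadir hemoglobin in cases where intraoperative transfusion was not performed".

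The only sensitivity analysis planned for a primary outcome compares the chosen definition with first transfusions only. It cannot apply to cases that were never transfused.

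**The concern.** Drawing a hemoglobin during surgery is a clinical choice, plausibly made more often when a low value is expected. The quarterly median among tested, non-transfused cases therefore depends on two things: how much anemia clinicians tolerate, and which patients they test. If testing spreads to lower-risk cases, the tested group becomes healthier and the median rises. If testing is cut back to higher-risk cases, the median falls. A constant overall rate with more selective testing also lowers it.

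This concerns which cases enter the outcome. It would remain even if every tested case had exactly one sample.

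The conclusion on one of two primary outcomes is at stake. A significant negative slope without inflection points would be taken as confirming the hypothesis when only testing had moved. In the other direction, a real fall could be cancelled by wider testing, and the aim would then be closed. The large sample makes this more acute, because small drifts become statistically significant.

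**Working it through.** **The plan's own figure.** The count of about 113,000 tested cases is a database query with no stated alpha, SD, effect size or power, so there is no calculation to reproduce. The study window, 1 January 2012 to 1 July 2017, contains 22 quarters, and 113,000 / 22 ≈ 5,136 tested cases per quarter, transfused and non-transfused together.

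**Inputs that are assumptions, not from the documents.** Nadir SD 1.8 g/dL; 4,500 tested non-transfused cases per quarter; correlation r between propensity to be tested and low hemoglobin of 0.2, 0.3 or 0.5; share tested 40% at the start.

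**Step 1: shift in the centre of the tested group.** Under bivariate-normal selection, the tested group lies r × 1.8 × λ(p) below the centre of all non-transfused cases. Here λ(p) = φ(z_p)/p, and p is the share tested.

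- λ(0.30) = 0.3477/0.30 = 1.159
- λ(0.40) = 0.3863/0.40 = 0.966
- λ(0.50) = 0.3989/0.50 = 0.798

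The change over the study is r × 1.8 × [λ(start) − λ(end)].

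**Step 2: sampling error of the total change.** The SE of one quarterly median is 1.2533 × 1.8/√4,500 = 0.0336. For 22 equally spaced quarters the sum of squares of time is 22 × (22² − 1)/12 = 885.5. The SE of the change over 21 steps is 21 × 0.0336/√885.5 ≈ 0.0237 g/dL.

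**Step 3: results with no change in practice.**

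| r | Testing 40% → 30% | z | Testing 40% → 50% | z |
|---|---|---|---|---|
| 0.2 | −0.07 g/dL | −2.9 | +0.06 g/dL | 2.5 |
| 0.3 | −0.10 g/dL | −4.4 | +0.09 g/dL | 3.8 |
| 0.5 | −0.17 g/dL | −7.3 | +0.15 g/dL | 6.4 |

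A smaller drop, from 40% to 35%, gives −0.03 (z = −1.4), −0.05 (z = −2.1) and −0.08 g/dL (z = −3.5). It is not significant at the weakest correlation.

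**Step 4: simulation of the protocol's test.** Ordinary regression of 22 quarterly medians on time, two-sided 0.05, 100 runs per scenario. Assumptions: 15,000 eligible non-transfused cases per quarter, nadir Normal(11.5, 1.8), values recorded to 0.1, and 30% tested at the start. The log-odds of being tested rise by b for each 1 g/dL lower hemoglobin.

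| True change (g/dL) | b | Share tested | Observed change (g/dL) | Significant fall |
|---|---|---|---|---|
| 0 | 0 | 30% → 20% | about 0 | 3% |
| 0 | 0.3 | 30% → 25% | −0.05 | 31% |
| 0 | 0.3 | 30% → 20% | −0.09 | 76% |
| 0 | 0.6 | 30% → 20% | −0.21 | 100% |
| 0 | 0.3 → 0.4 | constant 30% | −0.18 | 100% |
| −0.2 | 0.6 | constant 30% | −0.20 | 100% |
| −0.2 | 0.6 | 30% → 40% | −0.02 | 7% |
| −0.2 | 0.6 | 30% → 50% | +0.15 | 0% (significant rise in 100%) |

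Both errors appear, a fall that did not happen and a real fall that is missed. When testing is unrelated to hemoglobin (b = 0), a significant fall appears in only 0–3% of runs, whatever the testing rate.

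**The case against.** **An adjusted model is already planned.** Under Secondary Outcome 4 the protocol fits a multivariable linear model with intraoperative hemoglobin as the outcome, to examine whether practice changed over time. Its covariates include preoperative hemoglobin, specialty, age, ASA status and emergent surgery, and Statistical Analysis puts time into every model. If testing depends on those variables, this model can absorb much of the drift, so it would be wrong to infer that nothing planned bears on the problem. But the model is secondary, is fitted only where a hemoglobin exists, names a test of change over time only for transfused cases, and does not enter the primary decision rule. The institution-level analysis could expose a drift confined to some sites, but it uses the same tested-only median.

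**The outcome is the documented value.** The study is labelled descriptive, and its first aim concerns measured hemoglobin. A value seen and not acted on reflects tolerance of anemia, whereas an untested case offers no such value. This stands. A reader might infer that the right target is all non-transfused eligible cases, reached by weighting for the probability of being tested. The documents do not support that: it changes the quantity being estimated and risks extreme weights where testing is rare.

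**The size is assumed.** This also stands. Nothing in the protocol shows that testing changed, and the SD, testing shares and correlations are all supplied here. The SE of 0.024 holds only within-quarter sampling error. Season, site and case-mix scatter would enlarge it and lower every z.

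**It could wait for the SAP.** Added tables could. However, the protocol itself fixes the outcome, the unadjusted test and both decision rules, so the weakness lies in what it states.

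**Conclusion.** The point holds as a vulnerability of the primary decision rule. Primary Outcome 2 is observed only in tested cases, its slope is unadjusted, and a verdict on Hypothesis 1 is attached to that slope. Bias requires two conditions: testing must depend on expected hemoglobin, and the rate or selectivity of testing must change over the 22 quarters. Under the assumptions shown, a ten-point change in the share tested moves the median by 0.06–0.17 g/dL in either direction, several times the sampling SE. A five-point drop at weak correlation is not detectable.

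A reader might infer that testing did change, or that the result will be biased in a known direction. The protocol gives no testing rate, so neither can be said. Stable testing would leave the crude slope free of this particular bias, but no planned output is stated that would show whether testing was stable. The change should be made because a primary conclusion is exposed and the check is cheap.

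**What to change.** 1. Report, by quarter and by site, the share of eligible non-transfused cases with at least one intraoperative hemoglobin.
2. Keep the crude Primary Outcome 2 slope, and add a slope among tested non-transfused cases standardised to a fixed case mix, for example that of the whole-period tested population. Use variables already listed under Secondary Outcome 4 (preoperative hemoglobin, specialty, age, ASA status, emergent surgery) plus institution. Weighting to all eligible non-transfused cases can be an optional further sensitivity analysis.
3. Amend the rule as it applies to Primary Outcome 2. The nadir part of Hypothesis 1 is read as practice change only if the standardised slope is also negative with a 95% confidence interval excluding 0. A null crude slope does not close the aim until the standardised slope has been seen.

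The cost is one table and one further analysis. Because the Sample Size section presents its count of tested cases as an approximation of the inclusion criteria, the working extract may hold tested cases only. Step 1 would then need counts for untested cases, and the optional weighting would also need their covariates. Unrecorded reasons for testing remain uncorrected.

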The primary outcomes of this study are: the change in the pre-transfusion hemoglobin (ie transfusion threshold) and the nadir hemoglobin not-followed with an intraoperative transfusion over the course of the study period. The secondary outcomes of this study are: proportions of cases receiving a packed red blood cell transfusion throughout the study period (including stratification by prior laboratory measurements); the number of units of packed red blood cells transfused during the intraoperative period; the nadir postoperative hemoglobin (lowest value measured 0 – 72 hrs after the completion of intraoperative anesthesia care), the relationship between patient, surgical and institutional factors and the occurrence of transfusion and determination of the subsequent impact of any transfusion trends on blood product utilization; the relationship between in hospital mortality, post-operative myocardial injury, acute kidney injury and the pre-transfusion hemoglobin (for transfused cases – definition below) and lowest (for non-transfused cases) intraoperative hemoglobin.

In this study, we define coronary artery disease based on the present of a discharge ICD9/10 as listed in Appendix 3. Determination of AKI was based on the KIDIGO laboratory based definition AKI (Cr rise of 0.3 mg/dL rise within 48hrs of anesthesia end time or rise by more than 50% in 7 days). We will use intraoperative hemoglobin values documented, regardless of method of measurement. We preferentially use hemoglobin measures over hematocrit if these are documented simultaneously. If only a hematocrit is present at the time of lab measurement, we will perform an estimated conversion to hemoglobin, by dividing by 3. For blood transfusions documented exclusively in volume based units, we will convert this to units by assuming that any blood volume transfused greater than or equal to 250ml and less than or equal to 450 ml in one charting increment corresponds to one unit of blood.

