### **Statistical Analysis:**

Summary statistics will be presented as means and standard deviations or medians with interquartile ranges for continuous variables, as appropriate, and frequencies with percentages for categorical variables. All continuous variables will be assessed for normality using the Kolmogorov-Smirnov test. Univariate demographic and covariate comparisons between those who did and did not receive a transfusion will be analyzed using Student’s t-tests or Mann-

Whitney U tests for continuous variables, and Chi-squared or Fisher's Exact tests for categorical variables, as appropriate.

Mixed-effects multivariable linear or logistic regression models will be constructed as necessary. Prior to model entry, all covariates selected for model inclusion will be checked for collinearity using a Pearson correlation matrix. Variable pairs with a correlation  $> 0.70$  will be considered collinear and either combined into one variable, or one of the covariates will be excluded from the model. All variable pairs with a correlation  $\leq 0.70$  will be deemed fit for model entry. Model effect size will be presented as adjusted odds ratios with 95% confidence intervals, or beta coefficients with standard error, as appropriate. The covariates to be included in all models (discussed below) are surgical specialty, age, BMI, sex, presence of coronary artery disease, Elixhauser comorbidities, quarter of the study period, and hemoglobin. Time will be included in all models as a fixed effect by quarter, half-year, or year based on available sample size. The first quarter, half-year, or year will serve as the reference group. The random effects of institution and attending, where appropriate, will be presented as intraclass correlation coefficients and median odds ratios with 95% confidence intervals. Measures of effect size will be reported as adjusted odds ratios for logistic regression and beta coefficients for linear regression, and will be presented with 95% confidence intervals. For logistic regression models, model predictive capability will be presented as the area under the receiver operating curve (ROC) c-statistic. For linear regression, the extent to which the model explains the variability of the data will be presented as  $R^2$  values. Covariates with a statistically significant adjusted odds ratio or beta coefficient (as appropriate) will be considered independent predictors of the outcome.

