**Secondary Outcome 2: The number of units of packed red blood cells transfused during the intraoperative period.**

The number of units of pRBC transfused during the intraoperative period will be analyzed similar to Primary Outcome 1.

To determine independent predictors of the number of units of pRBC transfused during a case, two mixed effects linear regression models will be constructed with the independent covariates listed in the methods and the dependent variable of number of units of packed red blood cells transfused. The first model will contain the mixed effect of institution, and the second model will contain the hierarchical mixed effects of primary attending nested within institution.

**Secondary Outcome 3: The nadir postoperative hemoglobin (lowest value measured 0 – 72 hrs after the completion of intraoperative anesthesia care)**

The lowest postop hemoglobin will be examined for a trend over time for all cases using a Joinpoint analysis as for previous outcomes. The lowest postop hemoglobin will be compared at each time point between those with and without an intraoperative transfusion using a Student's t test or Mann-Whitney U test, as appropriate.

**Secondary Outcome 4: The relationship between patient, surgical and institutional factors and the occurrence of transfusion and determination of the subsequent impact of any transfusion trends on blood product utilization.**

Two mixed-effects logistic regression models will be used to determine if surgery type, year, and cardiac disease are independent predictors of intraoperative transfusion. The outcome of intraoperative transfusion will be defined as any PRBC use between Anesthesia Start and

Anesthesia End. The first model will contain the mixed effect of institution, and the second model will contain the hierarchical mixed effects of primary attending nested within institution. Independent variables to be included in the model are: Age, Sex, Elixhauser co-morbidities (as numeric and also CAD y/n, heart failure y/n, cancer y/n), WHO BMI classifications, ASA Status, Pre-op Hb, lowest Intra-op Hb for cases without intraop transfusion or the pre-transfusion hemoglobin, Pre-op Plts (abnormal y/n), Pre-op Creatinine (abnormal y/n), Abnormal coags (y/n – PT, PTT or INR), Surgical Specialty, EBL, Cell saver (Scavenged) blood use (y/n), Emergent Surgery, Use of anti-fibrinolytics (Aminocaproic Acid, Tranexamic Acid, Aprotinin) – y/n, and surgical Case Duration.

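### Primary Outcome 2 tests the nadir hemoglobin trend on time alone, so a small drift in pre-operative hemoglobin could create or hide a result that is then read as a change in transfusion practice

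*Protocol*

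**What the plan says.** In the Protocol, Primary Outcome 1 is tested "using a bivariate linear regression model with the dependent variable of median pre-transfusion hemoglobin measurement", with calendar quarter as the only predictor. A non-significant slope closes the analyses for that aim. Otherwise Joinpoint follows, and: "If no inflection points are found and the slope is negative and significantly different from 0, then Hypothesis 1 will be assumed true". Primary Outcome 2, the lowest intraoperative hemoglobin in cases not transfused, takes over the whole procedure: "The analysis for this outcome will be conducted identical to that for Primary Outcome 1". Its part of Hypothesis 1 (Introduction) is a "reduction in nadir hemoglobin in cases where intraoperative transfusion was not performed".

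Pre-operative hemoglobin is available. The covariates under Secondary Outcome 4 include "ASA Status, Pre-op Hb, lowest Intra-op Hb for cases without intraop transfusion or the pre-transfusion hemoglobin". The lists meant for all models do not name it: Statistical Analysis ends its list with "presence of coronary artery disease, Elixhauser comorbidities, quarter of the study period, and hemoglobin", and Methods has the nadir hemoglobin in that place.

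Secondary Outcome 4 also plans a linear model of intraoperative hemoglobin in transfused and non-transfused cases together, built on the earlier covariate list plus transfusion yes/no. Its stated test over time concerns transfused cases only. The one sensitivity analysis stated for Primary Outcome 1 concerns which transfusion of a case supplies the hemoglobin value.

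**The concern.** In a case without transfusion, the nadir is the starting hemoglobin minus the intraoperative fall. If patients arrive with a slightly lower or higher hemoglobin over the years, the nadir moves with them although no transfusion decision has changed. The Introduction asks how evidence for restrictive transfusion has translated into intraoperative practice, so a significant negative nadir slope will readily be taken as an answer to that question.

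The error can go either way. Falling starting hemoglobin can produce a significant negative slope with practice unchanged. Rising starting hemoglobin can cancel a real fall, and the rule then ends this outcome's trend analysis. With several thousand cases per quarter, the crude test is sensitive to very small shifts.

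**Working it through.** **Plan's own figure.** Sample Size gives about 113,000 cases as a database count. No alpha, power, effect or SD accompanies it, so there is no calculation to reproduce.

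**Inputs from the Protocol.** January 1, 2012 to July 1, 2017 is 5.5 years, or 22 quarters. 113,000 / 22 = 5,136 cases per quarter.

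**Assumed inputs.** Two-sided 5% test; 80-90% non-transfused (4,109-4,623 per quarter); nadir SD 1.5-1.8 g/dL; a linear drift of 0.10 g/dL in mean starting hemoglobin over the period; 50-70% of it passed to the nadir, so a spurious change of 0.05-0.07 g/dL.

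**Sampling error only**
- SE of a quarterly median = 1.2533 × SD / √n. This is 1.2533 × 1.5 / √4,623 = 0.0277 at the low end and 1.2533 × 1.8 / √4,109 = 0.0352 at the high end.
- Sum of squares of the quarter index: 22 × (22² − 1) / 12 = 885.5.
- SE of the fitted change over 21 quarter steps = 21 × SE(median) / √885.5 = 0.706 × SE(median), or 0.020-0.025 g/dL.
- Noncentrality runs from 0.05 / 0.0248 ≈ 2.0 to 0.07 / 0.0195 ≈ 3.6. From the noncentral t with 20 df, the probability of a significant slope is **48% to 93%**.
- A drift of 0.15 g/dL gives 82% to 100%.

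**With quarter-to-quarter scatter of SD 0.05 g/dL**
- SE of a quarterly value: √(0.0277² + 0.05²) = 0.057 to √(0.0352² + 0.05²) = 0.061.
- SE of the change: 0.040-0.043 g/dL.
- Probability of a significant slope: **20% to 38%**. With scatter SD 0.03 g/dL it is 31% to 64%.

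**Case-level simulation.** 200 runs per scenario, no quarter-level scatter. Assumed values: pre-operative hemoglobin mean 12.5, SD 1.9; mean fall about 2.0; transfusion when the nadir is below a trigger with mean 8.0, SD 0.8 (all g/dL). The adjusted comparator is a case-level regression on time and pre-operative hemoglobin.

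| Trigger change | Starting-Hb drift | Protocol's test significant | Adjusted test significant |
|---|---|---|---|
| none | −0.1 | 80% | 4% |
| none | −0.2 | 99.5% | 7% |
| −0.3 | none | 77% | 87.5% |
| −0.3 | +0.1 | 2.5% | 84% |
| −0.3 | +0.2 | 88%, slope positive | 86% |

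With the trigger lowered by 0.3, the crude nadir change without drift was −0.073 g/dL. The adjusted change was about −0.034 and stayed near that value whatever the drift. The adjusted slope is thus a smaller quantity than the crude one, but a stable one.

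**Primary Outcome 1.** The simulated correlation with pre-operative hemoglobin was about 0.36. The SE ratio is √(1 − 0.36²) = 0.933, a cut of about 7%; power of 70% would become about 76%. A drift of −0.2 moved the slope by only −0.04 g/dL and was significant in 15% of runs.

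**Check on the remedy.** A case-level model with institution as its only random effect ignores quarter-level scatter. With scatter SD 0.03-0.05 g/dL and a correlation of 0.5-0.7, its SE is too small by the factor √[s² / (s² + scatter²)], where s² = SD²(1 − ρ²)/n. Its false-positive rate is then about 22-56%. A regression on 22 adjusted quarterly values takes its error from that scatter and avoids this, provided the scatter is independent between quarters.

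**The case against.** The strongest reply is that the study is labelled descriptive and that Primary Outcome 2 concerns a documented value. If starting hemoglobin falls and the nadir falls with it, the nadir part of Hypothesis 1 is literally true. That stands: the crude slope is a correct description.

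A reader might also infer that the protocol calls the nadir a transfusion threshold. It does not. Methods lists the primary outcomes as "the change in the pre-transfusion hemoglobin (ie transfusion threshold) and the nadir hemoglobin not-followed with an intraoperative transfusion", and the label belongs to the pre-transfusion value. The Introduction's proxy wording is likewise attached to that value.

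A reader might infer that a drift took place. The protocol offers no evidence of one. That sites are surveyed on whether "pre-operative preparation strategies were routinely used" shows only that such practice was thought worth recording.

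The linear model under Secondary Outcome 4 is introduced to answer whether practice changed, and time is a fixed effect in all models. It can be read to include pre-operative hemoglobin, and its pooled time coefficient would be driven mainly by non-transfused cases. This softens the point but does not remove it: the stated time test is for transfused cases, and the model does not feed the decision rule.

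Nor does a null slope stop the study. It ends that outcome's own follow-on steps; nothing makes the secondary analyses conditional on it. Finally, other case-mix shifts of 0.05-0.07 g/dL would have the same effect, so pre-operative hemoglobin is not the only possible source. It is the most direct one, and it is already to hand.

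**Conclusion.** The point holds for Primary Outcome 2 and for the practice interpretation only. The decision rests on a time-only slope, and no planned test gives an adjusted time trend in non-transfused cases. A 0.10 g/dL drift in starting hemoglobin would be declared significant in 48-93% of studies with sampling error only, and in about 20-38% with quarter-level scatter of SD 0.05 g/dL, against a nominal 5%. Every SD, pass-through fraction, scatter value and drift behind these figures is assumed.

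The stronger reading, that both primary tests are compromised, is not supported. For Primary Outcome 1 the simulated bias is small and the gain in precision minor, and it vanishes if quarter-level scatter dominates. Nor do the documents support calling the crude nadir trend wrong or replacing it. A separate statistical analysis plan was not available; the point concerns what the Protocol itself fixes. The change is worth making because it is specific and cheap.

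**What to change.** Under Primary Outcome 2, prespecify a trend adjusted for pre-operative hemoglobin, and state that a nadir trend will be read as a change in practice only if this analysis supports it:

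1. From a case-level model, estimate the quarterly nadir hemoglobin adjusted for continuous pre-operative hemoglobin and institution.
2. Test the slope, and run Joinpoint, on the 22 adjusted quarterly values. Alternatively, include a random quarter effect in the case-level model. Either way, quarter-level scatter enters the standard error.
3. Keep the crude quarterly medians as the descriptive result, and show pre-operative hemoglobin by quarter beside them.

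The same adjustment is optional for Primary Outcome 1.

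The cost is some protocol wording and one more model on a variable already planned for extraction. The adjusted estimate is based on means rather than medians. Cases without a pre-operative value need a complete-case or imputation sensitivity analysis. The adjustment does not deal with drift in other factors, such as specialty, blood loss or which cases have an intraoperative measurement, and the report should say so.
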